Ticagrelor (Brilinta) is a new drug approved for use in patients with acute coronary syndrome to reduce the rate of thrombotic cardiovascular events. Early studies (please see investigator brochure for more information) showed that Ticagrelor achieves a higher inhibition of platelet aggregation as compared to Clopidogrel. The primary route of Ticagrelor elimination is via liver metabolism, thus, does not require dose adjustment in patients with renal impairments. Since Ticagrelor has not been used in hemodialysis patients for the purpose of preventing thrombosis in dialysis vascular accesses (Arterio-Venous Fistulae and Grafts), this study is designed as a pilot study to evaluate the feasibility and safety of Ticagrelor in hemodialysis patients with AVF vascular access to see if the treatment efficacy of Ticagrelor can preserve patency of hemodialysis vascular access better than Placebo.

Objectives: The primary objective is to evaluate the feasibility and safety of Ticagrelor in hemodialysis patients with AVF vascular access. The secondary objective is to evaluate the treatment efficacy in that whether Ticagrelor will preserve patency of hemodialysis vascular access better than Placebo. **Hypothesis:** Ticagrelor is safe and will preserve patency of hemodialysis vascular access (Arterio-Venous Fistulae) better than Placebo

The drug Ticagrelor, approved by FDA for patients with ACS, was never tested in patients with ESRD. In addition, if proven safe and effective in maintaining the patency of vascular access in patients with ESRD, which will be a new indication for the drug and hopefully will help, patients with ESRD maintain the patency of their access

Hypothesis to be Tested

Hypothesis: Ticagrelor is safe and will preserve patency of hemodialysis Arterio-Venous Fistulae better than Placebo. This is a Randomized, Placebo-controlled, Single Blind clinical trial. Seventy patients with ESRD on chronic HD and a functioning AVF will be recruited. Consent form will be obtained. History and physical, dialysis parameters and laboratory data will be obtained. Patients will be randomized into two groups to receive: Group 1: Ticagrelor 90 mg PO BID Group 2: Placebo drug PO BID Patients will be seen twice a month while on study treatment. We will assess any side effects and the relation to the study drug. -Clinical monitoring -Document adherence to the study -Document hospitalization with cause. -A monthly intra-access

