Due to the pilot nature of this study, formal power analysis and sample size estimation is not essential. Nevertheless, we attempted to estimate the potential treatment efficacy in this study. We considered the outcome measure for efficacy evaluation is the time to first stenosis event during the study period. From our recent clinical data, it was estimated that approximately 36% of dialysis patients experienced stenosis event at one-year follow-up. We would expect that patients in the new drug arm would have 10% stenosis event rate at one-year follow-up, compared to the 36% stenosis event rate in the placebo group. With these considerations, the analysis of stenosis-free survival will require at least 21 events, which is the number of events needed for one-sided log-rank test at 5% significance level to have 80% power to show statistically significant difference when the true hazard ratio is 0.236. This estimation will result in that approximately seventy patients will be needed and evenly randomized into each study arm (35 patients in Ticagrelor and 35 in placebo). This is an open-label study. Upon completion of all the required screening assessments, eligible patients will be randomly assigned to the study drug or placebo at 1:1 ratio with a block size of 20 in accordance with the randomization schedule. The randomization schedule will be provided by the Department of Public Health, School of Medicine. Patients will be identified by unique subject identifier that will remain consistent for the duration of the study. The active study period is 6 months followed by 6 months of monitoring, and accrual rate is approximately 12 patients per month. To compensate for an estimated drop-out rate of 25%, we will recruit 88 patients to the study.

4. What is your plan for primary variable analysis?

We have recruited/consented a total of 54 subjects into this study. We have enrolled a total of 43 patients into the study, 23 in the Ticagrelor treatment arm and 20 in the placebo arm. We will evaluate the safety of Ticagrelor in hemodialysis patients with AVF vascular access by tabulating adverse events and severe adverse events for the two study arms, and the difference between the two arms will be tested by chi-square test.

5. What is your plan for secondary variable analysis?

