For the secondary outcome, i.e., time to the first stenosis event, we will compare stenosis-free survival of Ticagrelor versus placebo using the Kaplan-Meier method. Survival probabilities and corresponding 95% confidence interval (CI) will be calculated at landmark time points for each arm, and survival difference between the two arms will be evaluated using a one-sided log-rank test stratified by the history of stenosis. Further, a stratified Cox proportional-hazards model will be used to derive the hazard ratio and 95% CI between the two regimens.

6. Have you been working with a statistician in designing this protocol?

Yes

IRB-HSR# 17224: Randomized, Placebo-controlled, Single Blind, Trial to Determine the Safety and Efficacy of Ticagrelor for Maintaining Patency of Arterio-Venous Fistulae Created for Hemodialysis

IF YES, what is their name?

[name]

Biomedical Research

1. What will be done in this protocol?

Subjects will be in this study for 1 year. Up to eighty eight patients with ESRD on chronic HD and a functioning AVF will be enrolled. For statistical purposes we will need to have seventy people complete the study. Consent form will be obtained. History and dialysis parameters will be taken at the screening visit. At the screening visit we will also be collecting a serum sample to perform a pregnancy test on female subjects of child bearing potential. This will be collected in a 3.5ml gold top serum separating tube. Study participants will be on the study medication (Ticagrelor) or placebo for six months (Visit 1 to Visit 12). Subjects will take the study medication twice a day. They will take it once in the morning and once in the evening. We will also instruct them to try and take it around the same times each day if possible. We will be collecting study medication to check for compliance at Visits 3, 6, 9, and 12. There will be a follow up for these subjects for six months (Visit 13 to Visit 18). Subjects will have a physical performed at screening, visit 12 (this is the last visit when subjects are on medicine), and at visit 18 which is the end of the study. We will be looking at hemoglobin levels that are collected as standard of care two times a month. We will be collecting the bleeding time weekly as well. This will be done at all visits (screening to Visit 18) which we define as the time it takes for a subjects' access to stop bleeding.

The following data will be documented on each subject at screening:

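### The primary safety comparison is a tabulation and a chi-square test with no confidence interval or margin, so a non-significant result in 43 patients could not support the hypothesis that ticagrelor is safe

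*Combined protocol and SAP*

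**What the plan says.** The objectives and item 2 of Statistical Considerations make feasibility and safety the primary objective. Efficacy is secondary. The hypothesis, in the background and under Hypothesis to be Tested, begins "Ticagrelor is safe and will preserve patency".

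Item 4 of Statistical Considerations holds the whole primary analysis. The first step is "tabulating adverse events and severe adverse events for the two study arms". A significance test follows: "the difference between the two arms will be tested by chi-square test". The same item gives the enrolment as "23 in the Ticagrelor treatment arm and 20 in the placebo arm".

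Item 3, the sample-size section, deals only with time to first stenosis. It planned "35 patients in Ticagrelor and 35 in placebo" and describes a "one-sided log-rank test at 5% significance level to have 80% power". It also says that formal power analysis is not essential because the study is a pilot. Item 5 plans 95% confidence intervals for the stenosis-free survival probabilities and for the hazard ratio.

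The Data and Safety Monitoring Plan describes the adverse events to be captured in three ways. Item 1.1 covers any undesirable sign or condition, related or not. Item 3.1 limits recording to events that are both related and serious. The text on reporting serious adverse events, after item 3.7, says that all of them will be documented whatever their cause.

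**The concern.** A test of no difference can give evidence of harm, but it cannot give evidence of safety. If it is not significant, the reader needs to know which excess risks the data rule out. Only an interval, or a margin fixed in advance, tells them that. The plan provides both an estimate and an interval for its secondary outcome, but only a table and a p-value for its primary one.

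At stake is the main conclusion of the trial. In a sample of this size, a non-significant p-value can arise because the drug does no harm, or because the trial could not have seen harm that is there. The planned output does not distinguish the two.

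**Working it through.** **Inputs from the documents.** The arm sizes are 23 and 20 (item 4), and the planned size is 35 per arm (item 3). The test is a chi-square test (item 4). The plan states no power for the safety test, so there is no figure of its own to reproduce.

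**Assumptions, because the documents are silent.** The test is two-sided at 5%. The chi-square is Pearson's, without continuity correction. The unit is the patient with at least one event. The placebo event rate is varied from 5% to 30%, and harm is expressed as a risk ratio of 2 or 3.

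**Power.** For each pair of counts a (ticagrelor, of n1) and b (placebo, of n2), with N = n1 + n2 and s = a + b:

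X² = N·[a(n2 − b) − b(n1 − a)]² / [n1·n2·s·(N − s)]

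Exact power is the sum of Bin(a; n1, p1)·Bin(b; n2, p0) over all pairs with X² > 3.841. The results for 23 against 20 are:

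| Assumed placebo rate | Power, risk doubled | Power, risk tripled |
|---|---|---|
| 5% | 3.0% | 11.1% |
| 10% | 11.5% | 34.7% |
| 15% | 19.7% | 58.3% |
| 20% | 29.2% | 79.4% |
| 25% | 40.1% | 93.3% |
| 30% | 53.0% | 99.3% |

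With 35 per arm and a 10% placebo rate, power is 21.9% for a doubling and 56.5% for a tripling. With 23 against 20 at 10%, a Yates correction lowers the figures to 6.0% and 23.7%, and Fisher's exact test gives 6.6% and 26.9%.

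**What an interval would add.** Take 5/23 against 2/20 as an illustration.

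- Risks: 5/23 = 0.217 and 2/20 = 0.100, so the difference is 0.117.
- Chi-square: X² = 43·(5·18 − 2·18)² / (23·20·7·36) = 43·54² / 115,920 = 1.08, so p = 0.30.
- Wilson 95% limits: 0.097 to 0.419 for ticagrelor, and 0.028 to 0.301 for placebo.
- Newcombe lower limit: 0.117 − √[(0.217 − 0.097)² + (0.301 − 0.100)²] = −0.117.
- Newcombe upper limit: 0.117 + √[(0.419 − 0.217)² + (0.100 − 0.028)²] = 0.332.

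The p-value says only that no difference was shown. The interval says that the data are compatible with anything from 12 points fewer to 33 points more patients with an event on ticagrelor.

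Nearly equal risks do not settle the matter either. For 2/23 against 2/20, p = 0.88, and the Newcombe interval is −22 to +18 points. With no events at all in 23 ticagrelor patients, the exact upper limit of the two-sided 95% interval is 1 − 0.025^(1/23) = 14.8%.

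**The case against.** Four points can be made for the plan.

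**It is a pilot and says so.** It disclaims formal power, so a small sample is not a hidden defect. This stands, and low power is not the fault raised here. But a pilot is a reason to estimate rather than to test, and its size does not make a test of no difference informative about safety.

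**The power depends on a rate that the documents do not give.** This also stands. A reader might infer that the test will usually miss even a tripling of risk. The documents do not support that as a general statement: in the table, power for a tripling is 58% at a 15% placebo rate and higher above that. Nor do they settle the rate. The broad definition in item 1.1 points to high rates, and the restriction in item 3.1 points to low ones.

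**The plan never says that p > 0.05 will be read as safe.** That is correct. A reader might infer such a rule from the hypothesis, but none is written, and the tabulation by arm is itself a descriptive analysis. What is missing is an interval and a statement of how a non-significant result will be read. Similarly, one might infer that events rather than patients will be counted, with repeat events treated as independent. The plan does not say that. It leaves the unit open.

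**Forty-three may not be the final number.** Item 4 reports enrolment to date, no section says that enrolment has closed, and 70 completers and 88 enrolled are still stated elsewhere. The larger sample raises power, but it leaves the inference problem in place.

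**Conclusion.** The concern holds as one about the form of the analysis. The primary safety comparison has no interval, margin or rule of interpretation, so a non-significant result could not support the stated hypothesis. This is true at any event rate and does not rest on the power figures.

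The size of the problem does rest on assumptions: a two-sided 5% level, an uncorrected chi-square, and 23 against 20 patients. Across placebo rates of 5% to 30%, power runs from 3% to 53% for a doubling of risk and from 11% to 99% for a tripling. At low event rates the test has little chance of showing even large relative harm. At higher rates it would usually detect a tripling, but at 25% or below it would still miss a doubling more often than not.

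The change is a cheap improvement that should be made. It is not a reason to question the conduct of the trial or its size.

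**What to change.** In item 4 of Statistical Considerations:

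- Make the primary safety result the number and percentage of patients per arm with at least one adverse event and, separately, with at least one severe adverse event. Give the risk difference and its Newcombe 95% confidence interval for each.
- Keep the chi-square p-value as descriptive, and state its level, its sidedness and whether it is corrected.
- State that a non-significant difference will not be read as evidence of safety.

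In the Data and Safety Monitoring Plan, reconcile item 1.1, item 3.1 and the text on reporting serious adverse events, so that it is clear which events are recorded. Until then, the numerator of the primary analysis is undefined.

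As an exploratory addition, the arms could be compared on data already collected, such as bleeding time ("We will be collecting the bleeding time weekly as well") and hemoglobin. This needs more care than the rest. The documents give hemoglobin as twice a month in one place and weekly in another. They give bleeding time as both weekly and at study visits, which are less frequent. Study drug is held or stopped on these same measures, so the summary must say how interruptions and withdrawals are handled.

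The main change costs a few lines and needs no new data. The downside is that the intervals will be wide and will show plainly how little the sample can rule out.

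### The landmark Kaplan-Meier estimates of time to first stenosis have no rule for death or kidney transplant, so they would modestly overstate actual stenosis risk; the log-rank test and Cox model stay valid

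*Combined protocol and SAP*

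**What the plan says.** Statistical Considerations, item 3 (sample size), states that "the outcome measure for efficacy evaluation is the time to first stenosis event during the study period". The trial is sized on stenosis rates alone: "approximately 36% of dialysis patients experienced stenosis event at one-year follow-up", against an expected 10% on ticagrelor, for a "one-sided log-rank test at 5% significance level to have 80% power" "when the true hazard ratio is 0.236".

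Item 5 (secondary variable analysis) names the same outcome and then says "we will compare stenosis-free survival of Ticagrelor versus placebo using the Kaplan-Meier method". It continues: "Survival probabilities and corresponding 95% confidence interval (CI) will be calculated at landmark time points for each arm". The arms are compared by a "one-sided log-rank test stratified by the history of stenosis", and "a stratified Cox proportional-hazards model will be used to derive the hazard ratio and 95% CI between the two regimens".

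Neither item says what happens to a patient who dies or is transplanted before a stenosis. Item 2 includes all randomized patients by intention to treat but sets no event or censoring rule. Drop-out is a single 25%, not divided by cause. Death appears in the safety definitions and reporting tables but in no analysis rule. Kidney transplant is not mentioned as a way of leaving follow-up. Participants are chronic hemodialysis patients aged up to 85, followed for a year, so both exits are foreseeable.

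**The concern.** A patient who dies, or who leaves hemodialysis after a transplant, can no longer have an access stenosis that counts in this trial. If such a patient is censored, Kaplan-Meier treats the patient as still at risk and shares that risk among those who remain. One minus Kaplan-Meier then estimates the stenosis risk in a hypothetical population where nobody dies or is transplanted. It is larger than the proportion who actually have a stenosis, and the curve itself is not the probability of being alive and free of stenosis.

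A second, looser issue is the label. Stenosis-free survival often means a composite of stenosis or death. Item 1 of Statistical Considerations says that investigators and study personnel will be un-blinded. A choice of event definition left open until analysis could therefore be made by people who know the allocation, in a trial with few events. At the reported enrolment of 23 v 20, the planning rates give 23 × 0.10 + 20 × 0.36 = 9.5 expected stenosis events.

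**Working it through.** **1. The plan's own hazard ratio.** With exponential times, HR = ln(1 − 0.10) / ln(1 − 0.36) = 0.1054 / 0.4463 = 0.236. This reproduces item 3 and uses stenosis rates only, so the planning calculation does not count death as an event.

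**2. Inputs for the check.**
- Stenosis hazards per year, from item 3: λ = 0.4463 (placebo) and 0.1054 (ticagrelor), treating 36% and 10% as net risks.
- Death or transplant: no figure in the documents. Assumed one-year risk d = 5% to 25%, equal in both arms, hazard μ = −ln(1 − d).

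**3. Censoring death and transplant.** One minus Kaplan-Meier at one year estimates 1 − e^(−λ), which stays at 36% and 10%. The actual cumulative incidence is λ/(λ+μ) × [1 − e^(−(λ+μ))]. For placebo at d = 25%: μ = 0.2877, and 0.4463/0.7340 × (1 − 0.64 × 0.75) = 0.608 × 0.52 = 31.6%.

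| Assumed d | Placebo, actual | Overstated by | Ticagrelor, actual | Overstated by |
|---|---|---|---|---|
| 5% | 35.2% | 0.8 points | 9.8% | 0.2 points |
| 10% | 34.3% | 1.7 points | 9.5% | 0.5 points |
| 15% | 33.4% | 2.6 points | 9.2% | 0.8 points |
| 20% | 32.5% | 3.5 points | 9.0% | 1.0 points |
| 25% | 31.6% | 4.4 points | 8.7% | 1.3 points |

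**4. If 36% is already a crude proportion.** The wording of item 3 allows this. The hazard is then slightly higher. At d = 25%, λ = 0.526 gives a cumulative incidence of 0.526/0.814 × (1 − e^(−0.814)) = 36%, while one minus Kaplan-Meier gives 1 − e^(−0.526) = 40.9%, an overstatement of 4.9 points. Direction and order of size do not change.

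**5. Size against sampling error.** The approximate 95% half-width around a placebo probability of 64% is 1.96 × √(0.64 × 0.36/20) = 21 points at 20 patients, and 1.96 × √(0.64 × 0.36/35) = 16 points at 35.

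**6. Effect of censoring on the test.** Simulated power of an unstratified one-sided 5% log-rank test, 10,000 runs, at 35 v 35: 85% with d = 0, 83% with d = 10%, 81% with d = 20%. At 23 v 20: 68%, 66% and 63%. The loss is small and comes from fewer stenosis events.

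**7. For comparison, counting death and transplant as events.** If the drug does not affect them, the composite hazard ratio is (0.1054 + μ)/(0.4463 + μ): 0.315 at d = 5%, 0.382 at 10%, 0.491 at 20% and 0.536 at 25%. Simulated power at 35 v 35 would be 70% at d = 10% and 56% at d = 20%. At 23 v 20 it would be 53% and 41%.

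**The case against.** The strongest reply is that the plan is clearer than the label suggests. Item 5 equates the secondary outcome with time to first stenosis in the same sentence that introduces stenosis-free survival, and item 3 sizes the trial on stenosis rates alone. On that text the label is simply the usual Kaplan-Meier term for remaining free of the event. This stands.

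A reader might infer from the label that the plan must suffer one of two harms, biased risks or a test aimed at a much weaker composite effect. The documents do not support that. The composite figures in step 7 show what a misreading would cost; they are not a consequence of the plan as written. They also depend on ticagrelor having no effect on death or transplant.

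Two further replies stand. Under censoring, the log-rank test and Cox model validly compare cause-specific stenosis hazards, so no fault lies in the planned comparison. The shift in the landmark estimates is also small: even 4.4 points is about a fifth of the 21-point half-width at 20 placebo patients. The plan promises survival probabilities, and the error arises when their complement is read as actual stenosis risk.

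What these replies do not remove is the missing rule. Nothing states that deaths and transplants are censored, and the complement of a landmark curve is commonly read as the risk patients face.

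**Conclusion.** The point holds in a limited form. The plan has no rule for death or kidney transplant. On the natural reading, that these patients are censored, the landmark estimates read as risks overstate actual one-year stenosis by about 0.8 to 4.4 points on placebo and 0.2 to 1.3 points on ticagrelor. That range rests on an assumed 5% to 25% death or transplant risk, equal in both arms, on exponential times, and on 36% and 10% being net risks. The top of the range is an extreme case, since 25% equals the protocol's whole allowance for screen failures, drop-outs and withdrawals.

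The stratified log-rank test and Cox hazard ratio are not called into question as cause-specific comparisons. The event definition still needs to be fixed before analysis, because counting deaths would break the link to the planning hazard ratio of 0.236 and staff know the allocation. The weight is minor: this is a secondary outcome of a pilot whose primary objective is feasibility and safety.

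**What to change.** In items 3 and 5 of Statistical Considerations:

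- State that the event is first confirmed stenosis, and that death and kidney transplant are competing events, not stenosis events.
- Report the landmark probabilities and 95% confidence intervals as cumulative incidence of stenosis, using the Aalen-Johansen estimator.
- Keep the stratified log-rank test and stratified Cox model, described as cause-specific comparisons with competing events censored.
- List deaths, transplants and withdrawals by arm beside the results. Withdrawals belong there because the bleeding rules can take patients out of the study, possibly more often in one arm, and censoring them could then be informative.

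If the sponsor intends a composite of stenosis or death instead, the plan should say so and recompute power for it.

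The cost is a few sentences, one extra standard estimator, and recording the date and reason for leaving dialysis or the study. The reported stenosis risks would be slightly lower.

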IRB-HSR# 17224: Randomized, Placebo-controlled, Single Blind, Trial to Determine the Safety and Efficacy of Ticagrelor for Maintaining Patency of Arterio-Venous Fistulae Created for Hemodialysis

► IF YES, who will generate the randomization scheme?

UVa Statistician: [name]

2. What are the statistical considerations for the protocol?

Since Ticagrelor has not been used in hemodialysis patients for the purpose of preventing thrombosis in dialysis vascular accesses (Arterio-Venous Fistulae and Grafts), this study is designed as a pilot study in that patients are randomly assigned to receive Ticagrelor or placebo drug for a six-month treatment period plus an additional 6-month follow-up period. The primary objective is to evaluate the feasibility and safety of Ticagrelor in hemodialysis patients with AVF vascular access. The secondary objective is to evaluate the treatment efficacy in that whether Ticagrelor will preserve patency of hemodialysis vascular access better than Placebo. The study will follow intent-to-treat principle and all randomized patients will be included in the analyses for the primary and secondary objectives.

3. Provide a justification for the sample size used in this protocol.

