1-Age/gender/race/body weight/cause of ESRD

2-Vintage of HD

3-Time since access was placed

4-Type and place of access and blood flow rate of access

5-History of prior access problems

6-Comorbid conditions (Example: Hypertension, coronary artery disease, Diabetes Mellitus, Bleeding problems, peripheral vascular disease).

7-Current medications (Example: Coumadin, Erythropoiesis stimulating agents, heparin, other antiplatelets, digoxin, statins)

This data will be obtained from the dialysis computer system and will be verified with the subject.

8-Physical Exam

9-Vital signs (blood pressure, heart rate, and weight) will be obtained from the subject's dialysis record.

Adverse events and concomitant medications will be reviewed at each study visit. We will also note any access issues at each study visit.

Study Medication Stopping Rules for Prolonged Bleeding:

If post treatment bleeding time is prolonged more than 30 minutes we will stop the study drug and refer for fistulogram,

If bleeding still persists after fistulogram and intervention we will continue to hold the study drug and do work up for bleeding. We will continue to hold study drug for 5 days if signs of increased tendency for bleeding as recurrent Epistaxis > twice in one week, if any evidence of GI bleed, or if Hgb should drop > 1gm in one week. If the bleeding is believed to be drug related or it no resolution occurs the subject will be withdrawn from the study.

We will also hold study drug for 5 days if hemoglobin is consistently less than 8g/dL for 2 consecutive weeks, or hemoglobin dropping 1g/dL in one week.

IRB-HSR# 17224: Randomized, Placebo-controlled, Single Blind, Trial to Determine the Safety and Efficacy of Ticagrelor for Maintaining Patency of Arterio-Venous Fistulae Created for Hemodialysis

For a prolonged bleeding event standard practice will be applied, including: (prolonged bleeding is defined as bleeding more than 30 minutes)

- **Direct pressure.** Any bleeding that warrants an emergency department visit should be immediately controlled with the application of direct digital pressure to the puncture site for 5-10 minutes. Once the bleeding abates, the patient should be observed for rebleeding or early thrombosis for 1-2 hours.

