- **Gelatin sponges.** Commonly seen in the emergency department as Gelfoam®, this adjunct may aid in the hemostasis of bleeding AV grafts. Although studies or case reports of this material being used in this setting are not found in the medical literature, our clinical practice has demonstrated success by including it in the management of this problem.

Life-Threatening Bleeding From Hemo Access

A vascular surgeon should be emergently consulted if hemorrhage cannot be quickly controlled. An adjunctive suture may be placed if there appears to be a small laceration of the graft rather than a puncture wound. This suture is used only after other measures to control bleeding described above have also failed.

Other life threatening bleeding: Subjects will be sent to the emergency department

2. Will you be using data/specimens in this study that were collected previously, with the use of a research consent form, from another research study?

No

3. List the procedures, in bullet form, that will be done for research as stipulated in this protocol.

- Physical Exams
- Administration of Investigational Drug
- HcG Blood Pregnancy Test
- Collection of Bleeding Time

Note: Laboratory data will be captured and recorded for research purposes from blood collected as part of the subject's clinical care-no additional blood is collected for the purpose of this study.

4. Will any of the procedures listed in item # 2 have the potential to identify an incidental finding?

Yes

► IF YES, check one of the following two options:

X The examination(s) utilize(s) the same techniques, equipment, etc., that would be used if the subject were to have the examination(s) performed for clinical care. There exists the potential for the discovery of clinically significant incidental findings.

- The PI takes full responsibility for the identification of incidental findings:
- The PI will inform the subjects verbally of all incidental findings that are of clinical significance or are of questionable significance.
- A follow-up letter describing the finding should be provided to the subject with instructions to either show the letter to their PC or if the subject has no PCP, the subject should be instructed to make an appointment at UVa or at the Free Clinic.

IRB-HSR# 17224: Randomized, Placebo-controlled, Single Blind, Trial to Determine the Safety and Efficacy of Ticagrelor for Maintaining Patency of Arterio-Venous Fistulae Created for Hemodialysis

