- Weekly Hemoglobin Tests

2.3 Under what criteria would an INDIVIDUAL SUBJECT’S study treatment or study participation be stopped or modified

At subject, PI or sponsor’s request

Treatment would be stopped if the subject had a serious adverse event deemed related to study

Subjects will be stopped if they meet one or more of the study stopping rules

2.4 Under what criteria would THE ENTIRE STUDY need to be stopped.

IRB-HSR# 17224: Randomized, Placebo-controlled, Single Blind, Trial to Determine the Safety and Efficacy of Ticagrelor for Maintaining Patency of Arterio-Venous Fistulae Created for Hemodialysis

*These are called stopping rules for early termination of the entire study.
List criteria regardless of whether the study is sponsored or not.
Be sure to include any criteria for which the UVa PI would halt the study at UVa.*

Per IRB, PI, DSMB, or sponsor discretion

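### Hemoglobin falls that lead the plan to hold study drug need not reach the by-arm safety comparison, although the values are already recorded

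*Combined protocol and SAP*

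**What the plan says.** Statistical Considerations, item 2: "The primary objective is to evaluate the feasibility and safety of Ticagrelor in hemodialysis patients with AVF vascular access". Efficacy is secondary. Item 4 gives the only safety analysis: "tabulating adverse events and severe adverse events for the two study arms, and the difference between the two arms will be tested by chi-square" test. Item 5 deals with efficacy alone: "For the secondary outcome, i.e., time to the first stenosis event". Neither item names a laboratory variable.

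Hemoglobin appears in several other places:

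- **Inclusion/Exclusion Criteria, item 2:** a last value below 9 g/dL excludes the patient.
- **Biomedical Research, item 1:** "We will be looking at hemoglobin levels that are collected as standard of care two times a month".
- **Data and Safety Monitoring Plan, 2.2:** "Weekly Hemoglobin Tests" is listed among the measures that reduce risk.
- **Biomedical Research, item 3, note:** "Laboratory data will be captured and recorded for research purposes", from blood drawn for clinical care.
- **Study Medication Stopping Rules for Prolonged Bleeding:** "We will also hold study drug for 5 days if hemoglobin is consistently less than 8g/dL for 2 consecutive weeks". A fall of 1 g/dL within a week has the same effect. The section also lists a weekly fall of more than 1 g, beside nosebleeds and gastrointestinal bleeding, as a sign of a tendency to bleed.

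Two further provisions matter. Data and Safety Monitoring Plan 3.1 says that not all adverse events will be recorded, only those judged both related and serious. Statistical Considerations, item 1, says that investigators and study personnel are unblinded.

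**The concern.** Bleeding heads the list of known complaints in Data and Safety Monitoring Plan 2.1, which also warns of severe bleeding. The plan acts on hemoglobin patient by patient but never sets the two arms side by side on it. Under 3.1, a fall that leads to a five-day hold enters the adverse event table only if someone who knows the arm judges it both serious and related.

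The needle-site bleeding time does not fill this gap. Biomedical Research, item 1, defines it as the time the access takes to stop bleeding, so it is a local measure and does not show gastrointestinal or other blood loss.

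At stake is a report of no safety difference while hemoglobin falls or drug holds were more frequent in one arm, with the values that would show it already on file.

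**Working it through.** The plan states no figure on this point, so there is none to reproduce. The check has a reading part and an arithmetic part.

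**1. Can a hold-triggering fall miss the comparison?**

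- Definition (Data and Safety Monitoring Plan 1.1): broad; any undesirable sign or condition counts, related or not.
- Recording (3.1): narrowed to related and serious.
- Serious events (Reporting of serious adverse events, under 3.7): all are documented, whatever the cause. This disagrees with 3.1 on relatedness but does not bring in non-serious falls.
- Analysis (Statistical Considerations, item 4): adverse event tables only.
- Aggregate review (5.3, 5.4): yearly, by the investigator. It covers adverse events, stopping rules, withdrawals and endpoint data, but specifies no comparison of hemoglobin by arm.

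A fall that leads to a hold but is not judged both serious and related therefore has no required route into the by-arm comparison.

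**2. Can the hold criteria be counted from the data?** Biomedical Research, item 1, has values twice a month; Data and Safety Monitoring Plan 2.2 has weekly tests. A one-week fall cannot be read from values about two weeks apart. The stopping rules also word the weekly fall in two ways (more than 1 g, and 1 g/dL).

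**3. What could a comparison of means detect?** Inputs: 23 and 20 patients (item 4); two-sided 5% level and 80% power; residual SD assumed, because the documents give none.

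Detectable difference = (1.960 + 0.842) × SD × √(1/23 + 1/20) = 2.802 × 0.3057 × SD = 0.857 × SD.

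| Assumed residual SD (g/dL) | Detectable difference (g/dL) |
|---|---|
| 0.5 | 0.43 |
| 0.8 | 0.69 |
| 1.0 | 0.86 |
| 1.25 | 1.07 |
| 1.5 | 1.28 |

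**4. What would a mean miss?** Suppose, for illustration, that 5 of 23 ticagrelor patients each lose 2 g/dL. If the loss lasts one of the six months, the arm's six-month mean moves by (5/23) × 2 × (1/6) = 0.07 g/dL. If it lasts three months, the mean moves by (5/23) × 2 × (3/6) = 0.22 g/dL. Both are below the smallest detectable difference in the table.

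**5. What would counts show?** With the uncorrected Pearson chi-square, the same five patients against none give 43 × (5×20 − 18×0)² / (5 × 38 × 23 × 20) = 430,000 / 87,400 = 4.92, p = 0.027. Four against none gives 275,200 / 71,760 = 3.835, p = 0.0502. With a continuity correction, five against none gives p = 0.082. Counts pick up episodic loss that a mean dilutes. At these numbers the p-value depends on the variant of the test, so an estimate with an exact interval is the better report.

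**The case against.** The strongest case on the other side is that this is a pilot with a broad definition of adverse events. Adverse events are reviewed at every visit, a bleeding-related fall meets the definition in 1.1, and the investigator's aggregate review covers stopping rules and withdrawals. On that view hemoglobin is already handled, and the real defect is the recording filter in 3.1. Part of this stands: the filter is what opens the gap, and a fall judged serious and related would still be tabulated. But as long as 3.1 applies, review at visits does not put a non-serious fall into the table, and the aggregate review specifies no by-arm hemoglobin comparison.

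A second objection is that a hemoglobin model could reassure falsely. Subjects whose bleeding is thought drug-related, or does not resolve, are withdrawn. Holds interrupt exposure, and erythropoiesis agents or transfusions can restore the value. All of these can pull the mean difference toward zero. This stands, and it is why counts should lead and the mean should only support them.

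A reader might also infer that a mean comparison is more sensitive than event counts because the detectable difference lies below the plan's 1 g/dL trigger. The documents do not support that. The trigger is one patient's fall within a week, the detectable difference concerns arm means over six months, and at the larger assumed SDs it exceeds 1 g/dL in any case. Step 4 shows that the ranking can reverse for episodic bleeding.

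**Conclusion.** The gap is real but limited. Under the plan as written, hemoglobin falls that are serious enough to hold study drug need not enter the primary safety comparison. It would be too strong to say that they cannot enter it, or that hemoglobin goes unwatched.

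No size of bias can be given, because the documents report neither event rates nor an SD. With 23 and 20 patients, the supporting mean comparison detects about 0.43 to 1.28 g/dL with 80% power. That range rests on assumed residual SDs of 0.5 to 1.5 g/dL and on all 43 patients contributing values. It should not be set against the 1 g/dL individual trigger, and a null mean difference must not be read alone as evidence of safety.

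This is a worthwhile, inexpensive improvement and not a flaw that undermines the trial.

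**What to change.** Add to Statistical Considerations, item 4, for the six on-drug months and all randomized patients:

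1. **Main addition.** The number of subjects per arm who met each hemoglobin criterion in the stopping rules, had study drug held for bleeding, or were withdrawn for bleeding. Give the risk difference and an exact 95% confidence interval for each.
2. **Support.** The between-arm difference in hemoglobin from a repeated-measures model adjusted for screening hemoglobin, with a 95% confidence interval. Keep values taken after a hold or stop wherever standard-of-care values exist.
3. **Context.** Use of erythropoiesis agents by arm, from the concomitant-medication review at each visit, and transfusions where recorded. The documents do not promise that transfusions or agent doses are captured; transfusion is mentioned only as an exclusion criterion.

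Reconcile the twice-monthly and weekly hemoglobin schedules, and the two wordings of the weekly fall, before the counts in (1) are defined. If only twice-monthly values exist, say that one-week falls cannot be counted. The hold rules themselves are not changed by this addition.

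The cost is about a paragraph of plan text and some extra analysis, with no new blood or visits. The downside is that the mean comparison can be diluted by erythropoiesis agents, transfusions, holds and withdrawals, so it should be reported only beside (1) and (3).
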